## **10.5 Reporting SAEs to Health Authorities and IECs / IRBs**

The Sponsor will inform the relevant health authorities of any reportable SAEs according to the local regulatory requirements. Reporting to the health authorities will be according to the Sponsor's standard operating procedures.

The Sponsor's RMO, [REDACTED], [REDACTED], [REDACTED], will notify the Investigators in writing of the occurrence of any reportable SAEs. The Investigators / Sponsor will be responsible for informing the IECs or IRBs that reviewed the trial protocol.

# **11 Data Collection and Management**

## **11.1 Data Collection and CRF Completion**

Individual safety diary cards, specifically designed for this trial by the Sponsor and provided to the study sites, will be given to study participants for the recording of daily safety information as described in [Section 9.3.2.3](#). These diary cards will include prelisted terms and intensity scales (see [Table 9.1](#) and [Table 9.2](#)) as well as areas for free text to capture additional safety information or other relevant details. Subjects or parents / guardians will also be provided with rulers for measuring the size of injection site reactions, and with standard digital thermometers for measuring daily temperatures. To ensure consistency of reporting, the study sites will instruct subjects or parents / guardians on how to correctly use these tools.

The 6-month follow-up will be done by interviewing subjects or parents / guardians either during a visit or over the telephone using a questionnaire to capture SAEs and AEs of particular interest, if applicable. An MA will be provided to the subjects at the preceding trial visit to help them record information on events occurring between this visit and the 6-month follow-up.

Relevant information will be transcribed into the CRF. Any SAEs captured during this 6-month follow-up period will be reported and followed-up as per the normal process for reporting SAEs.

The clinical team may decide to replace the MA by a diary card if a follow-up visit is planned for the subjects.

At specified intervals, the Investigator or an authorized designee will interview the subjects or parents / guardians to collect the information recorded in the diary card, and will attempt to clarify anything that is incomplete or unclear. All clinical trial information gathered by the study site will be reported electronically by the Investigator or authorized designee using a web-based CRF. (Any information that was not documented in the diary card will first be captured in the source

document and then reported electronically.) The CRF has been designed specifically for this trial under the responsibility of the Sponsor, using a validated Electronic Records / Electronic Signature-compliant platform (21 CFR Part 11).

To ensure the correct and consistent completion of the CRFs, the Sponsor or authorized representative will provide all necessary tools, instructions, and training to all site staff involved in data entry prior to study start. Additional instructional documents such as training manuals and completion guidelines will be provided to assist with data entry during the course of the trial.

Upon completion of training, each user requiring access to the EDC system will be issued a unique username and password. In the event of a change in trial personnel, each newly assigned individual will receive a unique username and password; the username and password of a previous user may not be reissued. If any trial personnel leave the study, the Investigator is responsible for informing the Sponsor immediately so that their access is deactivated. An audit trail will be initiated in the EDC system at the time of the first data entry in order to track all modifications and to ensure database integrity.

The Investigator is responsible for the timeliness, completeness, and accuracy of the information in the CRFs; must provide explanations for all missing information; and must sign the CRF using an e-signature.

## 11.2 Data Management

### *Management of Clinical Data*

Data generated during the trial will be managed following two different processes:

- Clinical data, defined as all data reported in the CRF, and laboratory data will be handled by the Sponsor's Clinical Data Management (CDM) platform or authorized representative.
- Data pertaining to SAEs, which are reported by the Investigator on the eSAE Forms or SAE Reporting Forms, will be handled by the Sponsor's GPV Department.

During the trial, clinical data reported in the CRFs will be integrated into the clinical database under the responsibility of the Sanofi Pasteur CDM platform. Data monitoring at the sites and quality control in the form of computerized logic and / or consistency checks will be systematically applied in order to detect errors or omissions. In addition, data reviews may be performed several times by the Sponsor's staff in the course of the trial. Any questions pertaining to the reported clinical data will be submitted to the investigator for resolution using the EDC system. Each step of this process will be monitored through the implementation of individual passwords to maintain appropriate database access and to ensure database integrity.

The validation of the immunogenicity data will be performed at the laboratory level following the laboratory's procedures. Information from the laboratory will be checked for consistency before integration into the clinical database.

After integration of all corrections in the complete set of data, and after the SAE information available from CDM and the GPV Department has been reconciled, the database will be released for statistical analysis.

### ***SAE Data Management***

During the trial, data pertaining to SAEs reported on eSAE Forms will be integrated into the Sponsor's centralized GPV database.

Upon receipt of an eSAE Form, the data will be entered into the GPV database after a duplicate check. Each SAE case will be assigned a case identification number. Each case will be entered in the GPV database and assessed by the case management platform or its delegate before being reported to the relevant authorities as necessary. Assessment of related cases will be done in collaboration with the PSO and the RMO. Follow-up information concerning a completed case will be entered into the GPV database, and a new version of the case will be created.

The information pertaining to SAEs in the GPV database will be reconciled with that in the clinical database.

### **11.3 Data Review**

A blind review of the data is anticipated through the data review process led by Data Management before database lock.

The safety of the investigational product will be continuously monitored by the Sponsor. Periodic safety data review will be performed by the Sponsor's SMT. For all periodic safety reviews, blinded safety data will be provided to the Sponsor's SMT.

## **12 Statistical Methods and Determination of Sample Size**

### **12.1 Statistical Methods**

Clinical data will be analyzed under the responsibility of the Biostatistics Platform of the Sponsor. A statistical analysis plan (SAP) will be written and peer reviewed before any analyses. In accordance with the protocol, the SAP will describe all analyses to be performed under the responsibility of the Sponsor and all the conventions to be taken.

#### **12.1.1 Hypotheses and Statistical Methods for Primary Objectives**

##### **12.1.1.1 Primary Objective 1**

##### ***Equivalence of 3 MenACYW Conjugate Vaccine Lots in Terms of hSBA GMTs***

Thirty days after the administration of the MenACYW conjugate vaccine, GMTs of antibodies against meningococcal serogroups A, C, Y, and W in Groups 1, 2, and 3 are equivalent.

Null hypothesis ( $H_0$ ):  $GMT_{(Gi)} / GMT_{(Gj)} \leq 1/2$  or  $GMT_{(Gi)} / GMT_{(Gj)} \geq 2$  for any  $i \neq j$

Alternative hypothesis ( $H_1$ ):  $1/2 < GMT_{(Gi)} / GMT_{(Gj)} < 2$  for all  $i \neq j$

$GMT_{(Gi)}$  and  $GMT_{(Gj)}$  are the GMTs of antibodies against the meningococcal serogroups A, C, Y, and W for the  $i$ th and  $j$ th lots, respectively. Each of the antigens of A, C, Y, and W serogroups

will be tested separately. If the 2-sided 95% confidence interval (CI) of the ratio of the GMTs is  $> 1/2$  and  $< 2$  for each antigen, the non-equivalence assumption will be rejected.

Assuming that  $\log_{10}$  transformation of the data follows a normal distribution, the  $\log_{10}$  (data) will be used for the statistical analysis, then antilog transformations will be applied to the results of calculations, in order to provide the results in terms of GMTs.

For each of the equivalence hypotheses using the GMT ratios, the statistical methodology will be based on the use of the 2-sided 95% CI of difference in means of post-vaccination  $\log_{10}$  transformed titers between the 2 groups with normal approximation.

### 12.1.1.2 Primary Objective 2

#### *Non-inferiority of MenACYW Conjugate Vaccine Compared to Menactra® in Terms of hSBA Vaccine Seroreponse*

Thirty days after the administration of MenACYW conjugate vaccine or Menactra®, the percentages of subjects who achieve an hSBA vaccine seroreponsea for meningococcal serogroups A, C, Y, and W in Groups 1, 2, and 3 combined are non-inferior to the corresponding percentages in Group 4.

Null hypothesis ( $H_0$ ):  $p_{(G123)} - p_{(G4)} \leq -10\%$

Alternative hypothesis ( $H_1$ ):  $p_{(G123)} - p_{(G4)} > -10\%$

where  $p_{(G123)}$  and  $p_{(G4)}$  are the percentages of subjects who achieve an hSBA vaccine seroreponse in Groups 1 - 3 pooled and Group 4, respectively. Each of the serogroups A, C, Y, and W will be tested separately. If the lower limit of the 2-sided 95% CI of the difference between the 2 proportions is  $> -10\%$ , the inferiority assumption will be rejected.

For the 4 non-inferiority hypotheses using the seroreponse rates, the CI of the difference in proportions will be computed using the Wilson Score method without continuity correction (35). The overall non-inferiority of this objective will be demonstrated if all 4 individual null hypotheses are rejected.

---

a hSBA vaccine seroreponse for serogroups A, C, Y, and W is defined as:

- For a subject with a pre-vaccination titer  $< 1:8$ , the post-vaccination titer must be  $\geq 1:16$ .
- For a subject with a pre-vaccination titer  $\geq 1:8$ , the post-vaccination titer must be at least 4-fold greater than the pre-vaccination titer.

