
Planned Sample Size:
	
A total of 3300 subjects are planned to be enrolled:
 
 
• Group 1: MenACYW conjugate vaccine (Lot 1): planned = 900 (evaluable = 810) 
 
• Group 1a: 400 subjects 10 to 17 years of age
 
• Group 1b: 500 subjects 18 to 55 years of age
 
 
 
• Group 2: MenACYW conjugate vaccine (Lot 2): planned = 900 (evaluable = 810) 
 
• Group 2a: 400 subjects 10 to 17 years of age
 
• Group 2b: 500 subjects 18 to 55 years of age
 
 
 
• Group 3: MenACYW conjugate vaccine (Lot 3): planned = 900 (evaluable = 810) 
 
• Group 3a: 400 subjects 10 to 17 years of age
 
• Group 3b: 500 subjects 18 to 55 years of age
 
 
 
• Group 4: Menactra®: planned = 600 (evaluable = 540) 
 
• Group 4a: 300 subjects 10 to 17 years of age
 
• Group 4b: 300 subjects 18 to 55 years of age
 
 
 
 
The planned number of subjects is based on a 10% dropout rate allowing around 88% power to reject the primary hypotheses simultaneously assuming the independence between each of the endpoints.

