5.1.1.2.1 Hypothesis

Non-inferiority of MenACYW Conjugate Vaccine Compared to Menactra[®] in Terms of hSBA Vaccine Seroresponse

Thirty days after the administration of MenACYW conjugate vaccine or Menactra[®], the percentages of subjects who achieve an hSBA vaccine seroresponse (as defined in Section 4.4.2.4) for meningococcal serogroups A, C, Y, and W in Groups 1, 2, and 3 combined are non-inferior to the corresponding percentages in Group 4.

Null hypothesis (H_0): $p_{(G123)} - p_{(G4)} \leq -10\%$

Alternative hypothesis (H_1): $p_{(G123)} - p_{(G4)} > -10\%$

where $p_{(G123)}$ and $p_{(G4)}$ are the percentages of subjects who achieve an hSBA vaccine seroresponse in Groups 1 - 3 pooled and Group 4, respectively.

Each of the serogroups A, C, Y, and W will be tested separately. If the lower limit of the 2-sided 95% CI of the difference between the 2 proportions is $> -10\%$, the inferiority assumption will be

rejected. The overall non-inferiority of this objective will be demonstrated if all 4 individual null hypotheses are rejected.

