5.1.1.2.2 Statistical Methods

For the 4 non-inferiority hypotheses using the seroresponse rates, the CI of the difference in proportions will be computed for each of the serogroups A, C, Y, and W using the Wilson Score method without continuity correction (8).

Let $\hat{\theta} = p_{123} - p_4$, then $L = \hat{\theta} - \delta$ and $U = \hat{\theta} + \varepsilon$ are respectively the lower and the upper limits of the CI, where:

$$\delta = Z_{0.025} \sqrt{\left\{ \frac{l_{123}(1-l_{123})}{n_{123}} + \frac{u_4(1-u_4)}{n_4} \right\}}$$

$$\varepsilon = Z_{0.025} \sqrt{\left\{ \frac{l_4(1-l_4)}{n_4} + \frac{u_{123}(1-u_{123})}{n_{123}} \right\}}$$

l_{123} and u_{123} are calculated from the CI of the pooled proportion in Group 1 - 3 given by:

$$\frac{(2n_{123}p_{123} + Z_{0.025}^2 \pm Z_{0.025} \sqrt{(Z_{0.025}^2 + 4n_{123}p_{123}(1-p_{123}))})}{2(n_{123} + Z_{0.025}^2)}$$

l_4 and u_4 are calculated from the CI of the single proportion in Group 4 given by:

$$\frac{(2n_4p_4 + Z_{0.025}^2 \pm Z_{0.025} \sqrt{(Z_{0.025}^2 + 4n_4p_4(1-p_4))})}{2(n_4 + Z_{0.025}^2)}$$

where $Z_{0.025}$ is the upper 97.5th percentile of the standard normal distribution,

$n_{123} = n_1 + n_2 + n_3$ is the total sample size of Groups 1 - 3,

$p_{123} = \frac{\text{total \# of seroresponders in groups 1 - 3}}{n_{123}}$ is the overall seroresponse rate of

Groups 1 - 3.

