5.1.2.1.2 Statistical Methods

For the 4 non-inferiority hypotheses using the seroresponse rates, the CI of the difference in proportions will be computed for each of the serogroups A, C, Y, and W using the Wilson Score method without continuity correction (8). The statistical method as described in Section 5.1.1.2.2 will be used to Groups 1b - 3b pooled and Group 4b.

5.1.2.2 Secondary Objective 2

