5.1.2.2.2 Statistical Methods

For the 4 non-inferiority hypotheses using the seroresponse rates, the CI of the difference in proportions will be computed for each of the serogroups A, C, Y, and W using the Wilson Score method without continuity correction (8). The statistical method as described in Section 5.1.1.2.2 will be used to Groups 1a - 3a pooled and Group 4a.

5.1.2.3 Secondary Objective 3

Comparison of 3 MenACYW Conjugate Vaccine Lots in Terms of hSBA Vaccine Seroresponse

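### The seroresponse non-inferiority intervals are valid but leave out baseline serostatus (hSBA below versus at or above 1:8), so they lose precision to the extent that response differs between those two strata

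*Protocol*

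**What the plan says.** Protocol 12.1.1.2 fixes the method for Primary Objective 2: "the CI of the difference in proportions will be computed using the Wilson Score method without continuity correction (35". Protocol 12.1.2.1 and 12.1.2.2 repeat it for adults and adolescents. SAP 5.1.1.2.2 has the interval "computed for each of the serogroups A, C, Y, and W using the Wilson Score method without continuity correction (8", with a formula that takes only the two overall rates and the two sample sizes. SAP 5.1.2.1.2 carries it to adults ("The statistical method as described in Section 5.1.1.2.2 will be used to Groups 1b - 3b pooled and Group 4b") and SAP 5.1.2.2.2 to adolescents ("The statistical method as described in Section 5.1.1.2.2 will be used to Groups 1a - 3a pooled and Group 4a"). The lower 95% limit must lie above -10 points, and "The overall non-inferiority of this objective will be demonstrated if all 4 individual null hypotheses are rejected".

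The endpoint has two branches (protocol 12.1.1.2, SAP 4.4.2.4). With a baseline below 1:8 the subject must reach 1:16. At or above 1:8, "the post-vaccination titer must be at least 4-fold greater than the pre-vaccination titer".

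Randomization is stratified by age only (protocol 6.5). The additional outputs in SAP 5.1.4 are by age group, gender and racial origin, or use the alternative analysis sets. No planned analysis, primary or supportive, stratifies by or adjusts for baseline titer.

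**The concern.** Baseline serostatus is fixed before randomization and is needed to score the endpoint, so using it in the analysis loses no subject. If subjects at or above 1:8 respond less often, the crude interval treats that predictable variation as noise. A chance excess of such subjects in one arm then moves the observed difference.

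The stakes are highest in the age-group objectives, which rest on about 270 evaluable Menactra subjects each. All four serogroups must pass, so small losses per serogroup multiply.

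**Working it through.** **Sample sizes.** The Synopsis gives "planned = 900 (evaluable = 810" per lot, and 600 planned with 540 evaluable for Menactra. The 10% dropout checks: 810/0.9 = 900 and 540/0.9 = 600. Pooled evaluable MenACYW is 3 x 810 = 2430. Applying 90% to the age cells (assuming equal dropout) gives 1350 versus 270 for adults and 1080 versus 270 for adolescents. The stated joint power of around 88% cannot be reproduced, because its inputs are blacked out.

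**Assumed inputs, not in the documents.** Overall seroresponse p = 70%; share at or above 1:8, f = 20-50%; response in that stratum lower by a gap g = 15-35 points.

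**Precision.** The share of variance explained by serostatus is R = f(1-f)g²/[p(1-p)], and the interval narrows by 1 - √(1-R). For f = 40%, g = 30: R = 0.24 x 0.09/0.21 = 10.3%, so it narrows by 5.3%.

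**Power.** 200,000 trials were simulated per scenario, comparing the crude interval with a stratified Newcombe interval whose weights are each stratum's share of both arms together. Adult objective, one serogroup, no true difference:

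| f, g | R | Narrowing by formula | Power, crude to stratified |
|---|---|---|---|
| 20%, 15 points | 1.7% | 0.9% | 93.0% to 93.8% |
| 30%, 20 points | 4.0% | 2.0% | 93.1% to 94.4% |
| 40%, 30 points | 10.3% | 5.3% | 93.1% to 95.5% |
| 50%, 35 points | 14.6% | 7.6% | 93.0% to 96.1% |

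- Adolescent objective: 91.9% to 92.7% at 20%/15 points and 91.8% to 94.5% at 40%/30 points; about 95% at the top of the range.
- Primary Objective 2 at no true difference: about 99.7% to at most 99.9%.
- Primary Objective 2 at a true 3-point shortfall: 91.0% to 91.7% at 20%/15 points and 91.0% to 93.8% at 40%/30 points; about 95% at the top.
- All four serogroups, if independent, at 40%/30 points: adults 0.931⁴ = 75% to 0.955⁴ = 83%; adolescents 0.918⁴ = 71% to 0.945⁴ = 80%. At 20%/15 points, adults 0.930⁴ = 75% to 0.938⁴ = 77%.

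**Chance imbalance.** The 95% shift in the crude difference is 1.96 x g x √[f(1-f)(1/n1 + 1/n2)].

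- Primary, low end: 1.96 x 0.15 x 0.40 x 0.0476 = 0.6 points. High end: 1.96 x 0.35 x 0.50 x 0.0476 = 1.6 points.
- Age groups: the last factor is 0.0667 (adults) or 0.0680 (adolescents), giving 0.8 to 2.3 points.

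**Error rate.** One-sided error at the margin is 2.6-2.7% crude and 2.7-2.9% stratified. Both are averages over randomizations.

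A separate set of assumptions shows the error given the imbalance that occurs: 80% response below 1:8, and 20%/20, 30%/30 or 50%/40 points, at 2430 versus 540. Given an imbalance of more than 1.5 standard deviations favouring MenACYW, the crude error at the margin is 5.5%, 8.2% or 10.9%. Given the opposite imbalance it is 1.0%, 0.5% or 0.1%. An imbalance that large in one given direction has a chance of about 6.7% (normal tail beyond 1.5).

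**Age.** Adolescents are 400/900 = 44.4% of each lot group but 300/600 = 50% of Group 4. This planned difference shifts the pooled crude difference by 0.0556 x 10 = 0.56 points for every 10-point age gap in seroresponse.

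**The case against.** The strongest reply is that nothing here is an error. The SAP gives a complete, reproducible formula for the stated hypothesis, a difference in overall percentages. Its unconditional coverage is 94.9-95.1%, because the crude interval already carries chance imbalance. That stands. A reader might infer that the tests are invalid or that their type I error is inflated; the documents and the calculations do not support this. The 5.5-10.9% error applies only given an unlucky allocation.

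Second, the benefit rests on assumed inputs. This also stands. A reader might infer from the two-part definition that the intervals are certainly too wide. But going from 1:4 to 1:16 and from 1:8 to 1:32 are both 4-fold rises. What changes at 1:8 is the fixed floor for lower baselines, so the definition alone settles neither the size nor, strictly, the direction of the response gap.

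Third, the gain is small at the low end, and for the primary objective it is negligible at no true difference. This is correct. Some of the low-end power difference also reflects a stratified interval that is slightly less conservative, as its error rate shows.

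Fourth, a supportive stratified analysis might suffice without changing the decision rule. That would meet the interpretive need, but it would leave the power gain in the age-group objectives unused.

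**Conclusion.** The point holds as a low-cost improvement to a valid plan. The three seroresponse objectives are decided without a prognostic split that the endpoint already uses, and no planned analysis would show whether a pass or fail owed something to baseline imbalance.

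Under the assumed ranges the narrowing is about 1-8%, and the benefit falls mainly on the two age-group objectives and on a primary comparison with a true shortfall. With no gap between strata there is essentially nothing to gain. The size therefore depends wholly on quantities the documents do not report.

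**What to change.** Before unblinding, amend protocol 12.1.1.2, 12.1.2.1 and 12.1.2.2 and SAP 5.1.1.2.2, 5.1.2.1.2 and 5.1.2.2.2 as follows.

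- Compute each serogroup's risk difference within that serogroup's baseline strata (hSBA below 1:8; at or above 1:8). For the pooled Primary Objective 2 comparison, also stratify by age group, the randomization stratum.
- Combine strata with weights equal to each stratum's share of both arms together, so that the target remains an overall difference to which the -10% margin applies.
- Use a stratified Newcombe interval, written out as fully as the present formula, and keep the -10% rule.
- Report the present crude interval as a sensitivity analysis.

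The cost is wording, a few lines of code and a slightly more complex formula. It needs no new data or extra subjects. If the decision rule cannot be changed, the minimum is the same stratified analysis pre-specified as supportive.

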## 12.1.2 Hypotheses and Statistical Methods for Secondary Objectives

### 12.1.2.1 Secondary Objective 1

#### ***Non-inferiority of MenACYW Conjugate Vaccine Compared to Menactra® in Terms of hSBA Vaccine Seroresponse in the Adult Population (18 to 55 Years Old)***

Thirty days after the administration of MenACYW conjugate vaccine or Menactra®, the percentages of subjects who achieve an hSBA vaccine seroresponsea for meningococcal serogroups A, C, Y, and W in Groups 1b, 2b, and 3b combined are non-inferior to the corresponding percentages in Group 4b.

Null hypothesis ( $H_0$ ):  $p_{(G123)} - p_{(G4)} \leq -10\%$

Alternative hypothesis ( $H_1$ ):  $p_{(G123)} - p_{(G4)} > -10\%$

where  $p_{(G123)}$  and  $p_{(G4)}$  are the percentages of subjects who achieve an hSBA vaccine seroresponse in Groups 1b, 2b, and 3b pooled and Group 4b, respectively. Each of the serogroups A, C, Y, and W will be tested separately. If the lower limit of the 2-sided 95% CI of the difference between the 2 proportions is  $> -10\%$ , the inferiority assumption will be rejected.

For the 4 non-inferiority hypotheses using the seroresponse rates, the CI of the difference in proportions will be computed using the Wilson Score method without continuity correction (35). The overall non-inferiority of this objective will be demonstrated if all 4 individual null hypotheses are rejected.

### 12.1.2.2 Secondary Objective 2

